## **Outcome Measures and Analysis:**

AUTO Study Protocol: Version Date: 12/22/21 PI: [name], MPH COMIRB No: 19-0059 Key measures in this trial (Table 3, additional details below) are tied directly to our theoretical framework (Figure 1) and assess DDA effects (Aim 1) and potentially differential subgroup effects (Aim 2).

Immediate outcomes: Our primary outcome will be the DDA's effect on decision quality, a fundamental element of the Ottawa Decision Support Framework as a precursor to behavior change (Figure 1). A high quality decision is defined as an informed patient making a decision consistent with their values.

-Decision Conflict: The Decisional Conflict Scale (DCS) measures internal conflict or ambivalence about the decision, with higher internal conflict (or ambivalence) indicating the decision is less in-line with personal values. The DCS is closely linked to overall decision quality and is a recommended primary outcome measure. The DCS estimates decisional conflict through personal perceptions of issues such as uncertainty in choosing options, modifiable factors contributing to uncertainty, and effective decision-making (e.g., expressing satisfaction with the choice). The DCS is a 16-item scale (with Likert scale response options) that has high reliability and test-retest correlation (Cronbach's alpha coefficients > 0.78). In prior work, the DCS has been shown to discriminate between known groups who make or delay decisions (effect size 0.4-0.8), with lower scores indicating low decision conflict (and greater likelihood of implementing a decision). Scores <25 (out of 100 total) are associated with implementing decisions.

-Values Concordance: We will use the "Values Clarity" subscale of the DCS to examine specifically how much participants feel their decisions are in line with their values. Three DCS items are summed and multiplied by 8.33; scores range from 0 (extremely clear) to 100 (extremely unclear about personal values).

-Knowledge: Questions will assess concepts about driving presented in the DDA and control group website.

-Self-Efficacy: We will measure decision self-efficacy (one's self-confidence or belief in one's ability to make decisions) using the Decision Self-Efficacy Scale, as decision aids can increase self-efficacy. Transformed scores range from 0 (extremely low) to 100 (extremely high self-efficacy).

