## AUTO Study Protocol: Version Date: 12/22/21 PI: [name], MPH COMIRB No: 19-0059 **Table 3. Key study measures**. Shown in relation to measurement point (pre- or post- DDA or website

Participant, and analytic plan. • = about self,  $\circ$  = as surrogate about older driver

		[name]/friends			Analytic Plan				
Domaiı	n and Key Measures	En	roll	F/u	Enr	oll	F/u			
		Pref	Post		Pre	Post			Hypoth.	Scoring
Immediate outcome										
Decision Conflict	Decisional Conflict Scale (DCS)	•	•	•	٠	•	•	1° Outcome	1a, 2a, 2b, 2c	Score <25
Knowledge	Knowledge questionnaire	•	•	•		•	•	2° Outcome	1a	Descriptive (cat.)
Values concordance	DCS Values Clarity subscale	٠	٠	•	٠	٠	٠	2° Outcome	1a	Descriptive (cat.)
Self-efficacy	Decision Self-Efficacy scale	•	•	•		•	•	2° Outcome	1a	Descriptive (contin.)
Longitudinal outcome										
Depression	PROMIS depression	٠		٠				2°	1b	T-score >50
								Covariate	1c	Descriptive (contin.)
Decision regret	Ottawa Decision Regret Scale			•			•	2° Outcome	1b	Descriptive (contin.)
Life space	Life-Space Assessment	٠		•			0	2° Outcome	1b	Descriptive (contin.)
Driving behaviors	Amount; reduction or cessation	•		•			0	2° Outcome	1c	Descriptive (cat.)
Subgroups										
Cognitive	5 minute MoCA			٠			•	Eligibility		Score ≥21
screening								Covariate	•	
Cognitive function	BTACT, OTMT	•						Stratify	2a	Normal vs. impaired
Insight	Beck Cognitive Insight Scale	٠		٠				Stratify	2a	R-C index ≥3
Decisional capacity	SPACED	•		•				Stratify	2b	# correct answers
Attitudes about	ARMT	٠		٠				Stratify	2c	Mean score ≥3.57
anning								Covariate	1c	_0.07

	Drivers	Family/fri	Analytic Plan				
Domaii	n and Key Measures	Enroll F	/u Enroll	F/u			
		PrePost	Pre Post			Hypoth.	Scoring
Other covariates							
Demographics	E.g., age, gender, race/ethnicity, marital/home status, education, income, urban/rural	•	• •	•	Covariate	all	Descriptive (cat.)
Physical health	Medical history, Activities of Daily Living, PROMIS global health	•	•	•	Covariate	all	Descriptive (cat.)
Mental health	PROMIS Emotional Support, Social Isolation; Perceived Stress Scale	•	•		Covariate	1b, 1c	Descriptive (cat.)
Personality	TIPI	•			Covariate	1c, 2c	Descriptive. (cat.)
Driving behaviors	Crashes, self-driving technologies	•	•	0	Covariate	1c	Descriptive (cat.)
Driving resources	Alternative transportation, support	•	••	• 0	Covariate	1c	Descriptive (cat.)
Driving education	Use of websites, courses, or other material driving or cessation	•	• •	•	Covariate	1c	Descriptive (cat.)

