Aim 1a. Test the DDA's effect on immediate decision quality (measured by the Decisional Conflict Scale). Hypothesis 1a: More DDA participants will have high-quality (DCS<25) scores, compared to control, immediately after the intervention. Our primary outcome measure will be the proportion of participants with DCS score <25. We will perform multiple logistic regression to test the DDA's effect on decision quality. We are also interested in jointly modeling the proportion of family members with DCS score <25, so a bivariate logistic regression model will be used for analysis to allow assessment of marginal effects of the intervention on patients and family members, as well as their concordance/discordance in decision quality. In the small pilot trial of Australian drivers with dementia, mean DCS score scores decreased from 22.5 to 7.5 (out of 100) after the DA; should we find that DCS score distributions do not allow dichotomization based on the cut-point of 25, we will instead compare means between the groups. Missing data for the primary measure should be minimal, given that this will be obtained at enrollment. Additional analyses will include examining components of decision quality to identify changes in

AUTO Study Protocol: Version Date: 12/22/21 PI: [name], MPH COMIRB No: 19-0059 measures like knowledge, values-concordance, or self-efficacy, as they may shed light on the mechanisms underlying decision-making about driving.

Family member data: In addition to the analysis under 1a, we will examine the degree of concordance (or discordance) within driver-family dyads on various measures, including current versus desired level of family involvement in driving retirement process (part of the driving questionnaire). To evaluate agreement we will look at the kappa coefficients at baseline and at follow-up points, as well as apply this class of repeated-measure concordance correlation coefficients. For longitudinal data, we will examine changes across the other time points (6, 12, 18, 24 months) using GEE after adjusting covariates.

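### Table 3 labels the 0-100 Values Clarity score, a secondary Aim 1a outcome, as categorical with no cut, reason or model; collapsing it would cost power and leave the boundary open

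*Combined protocol and SAP*

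**What the plan says.** Under Outcome Measures and Analysis, Values Clarity is a numeric score: "Three DCS items are summed and multiplied by 8.33; scores range from 0 (extremely clear) to 100 (extremely unclear about personal values". Decision self-efficacy is defined in the same list and also runs over 100 points: "Transformed scores range from 0 (extremely low) to 100 (extremely high self-efficacy". Knowledge gets one sentence, with no item count, total or range: "Questions will assess concepts about driving presented in the DDA and control group website".

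In Table 3, in the Scoring column of the analytic plan, the rows "DCS Values Clarity subscale" and "Knowledge questionnaire" are both secondary outcomes for hypothesis 1a with the entry "Descriptive (cat". Self-efficacy, also secondary for 1a, has "Descriptive (contin", as do decision regret (0-100) and life space (0-120) for 1b.

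The Aim 1a analysis text says that additional analyses will look at changes in "measures like knowledge, values-concordance, or self-efficacy, as they may shed light on the mechanisms underlying decision-making about driving". It gives no model, test, scale or cut for these components. Its fallback from a proportion to a comparison of means is written for the primary DCS score only, and the cut of 25 is stated for the total DCS only.

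**The concern.** Where Table 3 means to split a score, it usually prints the boundary: DCS below 25, depression T-score above 50, the insight index at 3, the ARMT mean at 3.57. Values Clarity is the only 0-100 outcome score marked categorical with no boundary beside it, and nothing elsewhere supplies one.

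Two things are at stake. First, grouping a graded score discards the ordering and distance within each group, which costs power. Second, with no boundary fixed in advance, whoever runs the analysis can choose it after seeing the data, and the finding may change with the choice. The protocol defines a high-quality decision as one that is informed and in line with the person's values, and it looks to this outcome to explain how the aid works. A mechanistic reading should not rest on an unplanned cut.

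**Working it through.** **The plan's own figure.** The documents give no SD, effect or power for Values Clarity. The nearest figure is the primary sample size of 300 (Sample Size section: 20-point difference, 90% power, 0.05, 10% loss). For 0.40 vs 0.60, two-sided:

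n per arm = [1.960·√(2·0.5·0.5) + 1.282·√(0.4·0.6 + 0.6·0.4)]² / 0.20² = (1.386 + 0.888)² / 0.04, which rounds up to 130. Then 2·130 / 0.9 = 289.

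The stated 300 is consistent with its inputs, and nothing below changes it.

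**Number of levels.** 8.33 × 12 = 99.96, so three items scored 0-4 give sums of 0 to 12, that is 13 levels. The 0-4 item scoring is inferred, not stated.

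**Arm size.** 150 per arm. The outcome is taken at enrolment, right after the intervention, so the 10% allowance for loss to follow-up is not applied.

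**Two-way split of a roughly normal score (assumption).** The shift with 80% power on the score is d = (1.960 + 0.842)·√(2/150) = 0.32 SD. If a share p1 of controls lies below the cut, the DDA share is p2 = Φ(Φ⁻¹(p1) + d). With p̄ = (p1 + p2)/2,

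power = Φ{ [p2 − p1 − 1.960·√(2p̄(1−p̄)/150)] / √([p1(1−p1) + p2(1−p2)]/150) }.

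For p1 = 0.50: p2 = 0.627 and (0.1268 − 1.960·0.0573)/0.0568 = 0.256, so power is 0.60. The efficiency column is φ(z)²/[p1(1−p1)] with z = Φ⁻¹(p1).

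| Control share below cut | DDA share | Power after split | Efficiency relative to score |
|---|---|---|---|
| 50% | 62.7% | 0.601 | 0.64 |
| 30% | 42.0% | 0.585 | 0.58 |
| 20% | 30.2% | 0.532 | 0.49 |
| 10% | 16.9% | 0.417 | 0.34 |
| 5% | 9.3% | 0.305 | 0.22 |

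**Check on a 13-level score.** Simulated with assumed SD 20, a shift of 0.35 SD (7 points), control mean 15, 25 or 40, and 150 per arm:

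| Analysis | Power |
|---|---|
| t-test on the score | 81-85% |
| Wilcoxon (all levels, ordered) | 81-84% |
| Two groups, item sum below 3 vs 3 or more | 58-71% |
| Three groups, chi-square | 59-66% |
| 13 unordered levels, chi-square | 43-45% |

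Moving the two-way cut matters. With control mean 40, fully clear (score 0) against the rest has about 29% power. Cuts further into a tail can be lower still.

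**Borrowing the total-DCS cut does not settle it.** An item sum of 3 becomes 3 × 8.33 = 24.99, so a literal below-25 rule counts it as low, although the unrounded value is 25. In the simulation, moving the cut by that one level changes power by roughly 4 to 9 points, up or down depending on the control mean.

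**Knowledge.** No calculation is possible: no score is defined.

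**The case against.** The strongest reply is that a table label is being over-read. The entry begins with the word for descriptive, the Aim 1a text commits to no test, and Table 3 uses the categorical label loosely. It covers demographics including age, and PROMIS support and isolation scores, although PROMIS scores are elsewhere said to be analysed as T-scores. This stands in part: a reader might infer that the plan has committed to an inferential categorical analysis, and the documents do not go that far. But those loose examples are covariate rows. Among outcome rows, regret and life space are marked continuous and get linear models under Aim 1b, while driving behaviors are marked categorical and get a logistic link under Aim 1c. The correspondence is imperfect, since depression has a T-score cut in Table 3 but falls under the linear models of Aim 1b. Still, nothing corrects the Values Clarity entry.

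Three further points stand in full:

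- A reader might infer that knowledge also loses score information. The documents define no knowledge score, and item-by-item correct/incorrect reporting would be naturally categorical.
- A reader might infer a guaranteed minimum loss of power. Categorical need not mean two groups, and an analysis that keeps the levels in order loses almost nothing.
- Adjusting for the pre-intervention score is not an advantage peculiar to continuous scoring; logistic and ordinal models can adjust too.

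A plea for comparability with self-efficacy would also be weak, since the instruments differ and run in opposite directions.

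**Conclusion.** The point holds for Values Clarity as a gap in specification with a probable cost. The scale is numeric, the label is categorical, and no boundary, reason or model is given. If the score is split in two, a shift with about 80% power on the score would have roughly 30-70% power, depending on the cut. That range rests on assumed distributions, an assumed shift of about a third of an SD, 150 per arm and two-sided 0.05; it illustrates the cost and does not predict it. The loss is close to nil if all levels are kept in order, and larger if they are treated as unordered.

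For knowledge the conclusion is narrower: scoring and categories are undefined, and no loss can be shown. Both are secondary, mechanism-oriented outcomes, so this is a worthwhile improvement and no threat to the trial's main result.

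**What to change.** - In Table 3, change the Values Clarity scoring entry to continuous.
- In the Aim 1a text, state that the drivers' immediate post-intervention Values Clarity score will be compared between arms, adjusted for the pre-intervention score that Table 3 already schedules. Name the model in advance: linear, reporting a mean difference with 95% CI, or ordinal if many scores are expected to pile up at the clear end.
- Keep any categories for display only, with boundaries written down before outcome data are examined by arm.
- For knowledge, state how the questionnaire is scored. If a total is formed, analyse it in the same way with baseline adjustment; if only item-level results are intended, say so.

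The cost is one table entry, a sentence or two of analysis text and a scoring rule for knowledge. It needs no new data collection.

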## AUTO Study Protocol: Version Date: 12/22/21 PI: [name], MPH COMIRB No: 19-0059 **Table 3. Key study measures**. Shown in relation to measurement point (pre- or post- DDA or website

Participant, and analytic plan. • = about self,  $\circ$  = as surrogate about older driver

		[name]/friends			Analytic Plan				
Domaiı	n and Key Measures	En	roll	F/u	Enr	oll	F/u			
		Pref	Post		Pre	Post			Hypoth.	Scoring
Immediate outcome										
Decision Conflict	Decisional Conflict Scale (DCS)	•	•	•	٠	•	•	1° Outcome	1a, 2a, 2b, 2c	Score <25
Knowledge	Knowledge questionnaire	•	•	•		•	•	2° Outcome	1a	Descriptive (cat.)
Values concordance	DCS Values Clarity subscale	٠	٠	•	٠	٠	٠	2° Outcome	1a	Descriptive (cat.)
Self-efficacy	Decision Self-Efficacy scale	•	•	•		•	•	2° Outcome	1a	Descriptive (contin.)
Longitudinal outcome										
Depression	PROMIS depression	٠		٠				2°	1b	T-score >50
								Covariate	1c	Descriptive (contin.)
Decision regret	Ottawa Decision Regret Scale			•			•	2° Outcome	1b	Descriptive (contin.)
Life space	Life-Space Assessment	٠		•			0	2° Outcome	1b	Descriptive (contin.)
Driving behaviors	Amount; reduction or cessation	•		•			0	2° Outcome	1c	Descriptive (cat.)
Subgroups										
Cognitive	5 minute MoCA			٠			•	Eligibility		Score ≥21
screening								Covariate	•	
Cognitive function	BTACT, OTMT	•						Stratify	2a	Normal vs. impaired
Insight	Beck Cognitive Insight Scale	٠		٠				Stratify	2a	R-C index ≥3
Decisional capacity	SPACED	•		•				Stratify	2b	# correct answers
Attitudes about	ARMT	٠		٠				Stratify	2c	Mean score ≥3.57
anning								Covariate	1c	_0.07

	Drivers	Family/fri	Analytic Plan				
Domaii	n and Key Measures	Enroll F	/u Enroll	F/u			
		PrePost	Pre Post			Hypoth.	Scoring
Other covariates							
Demographics	E.g., age, gender, race/ethnicity, marital/home status, education, income, urban/rural	•	• •	•	Covariate	all	Descriptive (cat.)
Physical health	Medical history, Activities of Daily Living, PROMIS global health	•	•	•	Covariate	all	Descriptive (cat.)
Mental health	PROMIS Emotional Support, Social Isolation; Perceived Stress Scale	•	•		Covariate	1b, 1c	Descriptive (cat.)
Personality	TIPI	•			Covariate	1c, 2c	Descriptive. (cat.)
Driving behaviors	Crashes, self-driving technologies	•	•	0	Covariate	1c	Descriptive (cat.)
Driving resources	Alternative transportation, support	•	••	• 0	Covariate	1c	Descriptive (cat.)
Driving education	Use of websites, courses, or other material driving or cessation	•	• •	•	Covariate	1c	Descriptive (cat.)
Family questionnaire	Relationship to driver, co- reliance		•	•	Covariate	1a	Descriptive (cat.)
Life Events	Major Life Events		•	•0	Covariate	all	Descriptive (cat.)
Coronavirus- related health	Coronavirus/COVID-19 Health/Exposure Status	•	• •	•			

Subgroups: Analyses will include stratification by cognitive and attitudinal factors.

-Cognitive function: At baseline we will administer the Brief Test of Adult Cognition by Telephone, which assesses episodic memory (word list recall immediate and delayed), Category verbal fluency, Backward digit span, 30-Second Counting task, Number series, Stop & GoSwitch Task, and Executive Functioning. We will augment the BTACT with the Oral Trail Making Test (OTMT). [name] will categorize participants' cognitive function as MCI, dementia or non-impaired based on the BTACT Composite and OTMT-B (z-score < -1.5 is impaired). [Note: initial study protocol included RBANS and TMT instead of BTACT and OTMT; see protocol version 10.14.19 for more details]

-Insight: The Beck Cognitive Insight Scale comprises two sub-scales (self-reflectiveness and self-certainty); the composite "R-C index" (self-reflectiveness score minus self-certainty score) reflects overall cognitive insight. In one study each sub-scale and the R-C index were lower in

AUTO Study Protocol: Version Date: 12/22/21 PI: [name], MPH COMIRB No: 19-0059 those with probable Alzheimer's disease compared to control. We will use a conservative cutoff, with <3 categorized as low insight.

-Decisional capacity: This construct is related to but distinct from cognitive ability. We will use the Short Portable ACED (SPACED) to measure understanding, appreciation, comparative reasoning, and consequential reasoning. Each of these four criteria are scored a 0 for inadequate, 1 for marginal, and 2 for adequate. This produces as total range of 0 to 8. In the end, participants can be dichotomized as those with 0s versus others, median split, 8's versus others, etc. Scores can also be used as a continuous outcome measure in regression models...

-Attitudes about driving: The ARMT measures affective and emotional aspects of present or future mobility changes associated with cessation. It has four subscales: anticipatory anxiety, perceived burden, avoidance, and adverse situation (i.e., the view that mobility loss is harmful to quality of life). Each of the 24 items is rated on a 1-5 Likert scale; high total average scores (mean >3.57) indicate low readiness to transition.

Other covariates: Additional measures are for eligibility screening, key covariates, and exploratory analyses.

-Cognitive screening: We will use the 5-minute Montreal Cognitive Assessment [MoCA] with a score <21 being an enrollment exclusion criterion due to the likelihood of poor driving ability and impaired decisional capacity. However, even individuals with MoCA scores ≥21 may have impaired decision-making capacity. If concerns arise during the consent process that the participant does not understand aspects of the study, the participant will not be enrolled in the study.

-Demographics: These will include basic demographic characteristics like age, gender, and residence (e.g., private residence vs senior apartment complex, alone vs with others, urban vs rural location).

-Physical and emotional health: These measures will include assistance for Activities of Daily Living (ADLs), medical comorbidities, and overall perceived health. Progressive medical conditions associated with reduced driving ability and increase risk of cessation (eligibility criterion, above) will be categorized by type (e.g., visual, cognitive or musculoskeletal) or particular diagnosis, depending on sample prevalence.

-Emotional health: We will also collect PROMIS measures of Emotional Support (4-item) and Social Isolation (4-item) and the 4-item Perceived Stress Scale.

-Personality: As personality may relate to driving (e.g., enjoyment versus anxiety with driving) we will use the Ten-Item Personality Inventory (TIPI), a shortened questionnaire for personality dimensions.

-Driving resources: Resources assessed will include access to and use of alternative transportation, interest in self-driving technologies, and emotional, financial or logistical support from others.

-Driving education: To assess possible control group contamination, at baseline and follow-up we will assess exposure to websites, videos, courses, or other educational resources about driving and driving cessation.

-Family member questionnaire: Questions will assess the relationship between the driver and family member, including frequency of contact and co-reliance for transportation (e.g., does older driver provide rides for family member's children, is family member available and willing to provide rides to older driver).

-Coronavirus/COVID-19 Health/Exposure Status (informed by the Coronavirus Health Impact Survey (CRISIS)): Questions will assess current impact of Coronavirus pandemic on physical and mental health, as well as other select domains (e.g., impact on important events, routine inperson activities, financial and living stability, etc).

Analysis for Aim 1: Analyses will be performed according to the principle of intention-to-treat. including all randomized drivers. Unless otherwise specified, hypothesis tests will be two-sided with alpha=.05, with 95% confidence intervals or p values reported. All canalyses will be performed using SAS/STAT® software. First, descriptive statistics will be computed for baseline patient characteristics, initially testing for differences between control and intervention groups (including for key covariates, Table 3.3). We will assess site effects by comparing demographic variables across the sites, using ANOVA for continuous measures and chi-square tests of proportions for categorical measures. If no statistically significant differences exist among sites. we will ignore site and formally test the differences in proportions or means as described below. If there are significant differences among sites, then (assuming enough events) we will use separate bivariate logistic regression models for each aim described below, with a fixed effect for site and with treatment arm as the main predictor. For longitudinal analyses, we will conduct logistic regression with unstructured correlation of generalized estimating equations (GEE) to account for the repeated observations for each participant. Statistical significance will be evaluated at one-sided p<.05 level. Analyses of the DDA's longitudinal effects may be vulnerable to bias, as control arm participants may be exposed to intervention arm messages through exposure to available materials or courses related to driving safety or cessation (e.g., websites, physician counseling, AARP courses). We will assess exposure to other sources of information through structured questions. To mitigate the impact of this potential bias, we will adjust measurements of contamination as applicable. In all analyses, validation of distributional and parameterization assumptions will be checked and data transformations (e.g. logtransformations) or alternative methods will be implemented as appropriate.

Aim 1a. Test the DDA's effect on immediate decision quality (measured by the Decisional Conflict Scale). Hypothesis 1a: More DDA participants will have high-quality (DCS<25) scores, compared to control, immediately after the intervention. Our primary outcome measure will be the proportion of participants with DCS score <25. We will perform multiple logistic regression to test the DDA's effect on decision quality. We are also interested in jointly modeling the proportion of family members with DCS score <25, so a bivariate logistic regression model will be used for analysis to allow assessment of marginal effects of the intervention on patients and family members, as well as their concordance/discordance in decision quality. In the small pilot trial of Australian drivers with dementia, mean DCS score scores decreased from 22.5 to 7.5 (out of 100) after the DA; should we find that DCS score distributions do not allow dichotomization based on the cut-point of 25, we will instead compare means between the groups. Missing data for the primary measure should be minimal, given that this will be obtained at enrollment. Additional analyses will include examining components of decision quality to identify changes in

AUTO Study Protocol: Version Date: 12/22/21 PI: [name], MPH COMIRB No: 19-0059 measures like knowledge, values-concordance, or self-efficacy, as they may shed light on the mechanisms underlying decision-making about driving.

Family member data: In addition to the analysis under 1a, we will examine the degree of concordance (or discordance) within driver-family dyads on various measures, including current versus desired level of family involvement in driving retirement process (part of the driving questionnaire). To evaluate agreement we will look at the kappa coefficients at baseline and at follow-up points, as well as apply this class of repeated-measure concordance correlation coefficients. For longitudinal data, we will examine changes across the other time points (6, 12, 18, 24 months) using GEE after adjusting covariates.

Aim 1b. Test the DDA's longitudinal effect on psychosocial outcomes at 12 and 24 months. Hypothesis 1b: Participants in the DDA group will have reduced prevalence of depressive symptoms and of decision regret but maintained life space, at 12 and 24 months after enrollment, compared to control participants. We will use descriptive statistics, including proportions with 95% CIs or medians and interquartile ranges, for comparison between treatment groups. We will utilize GEE with a linear link, and a linear mixed model (LMM) with a random intercept, fixed effects and a linear link for each outcome. We will adjust for baseline characteristics (gender, age, education, etc.), driving behaviors and other variables. We will perform sensitivity analyses to examine the missing assumption under maximum likelihood.

Aim 1c. Test the DDA's longitudinal effect on driving behaviors at 12 and 24 months. Exploratory: The DDA does not provide specific recommendations as to whether the participant should stop driving or not. We will compare the proportion of participants who change their reported driving behaviors (reduce driving or cease altogether) over the follow-up period to examine whether the DDA appears to affect them. We will apply GEE with a logistic link, and a generalized LMM (GLMM) with a random intercept and a logistic link for each outcome. Also, we will adjust demographic variables and appropriate variables.

Secondary analyses: Secondary analyses by gender will be conducted, as we hypothesize there will be differences in behavior and outcomes based on gender, and the belief that the responses to DDA intervention may be heterogeneous between men and women. Aim 1a-1c will be considered gender analyses using logistic regression and GLMM. We will also examine the degree of concordance (or discordance) within driver-family dyads on various measures, including DCS and current versus desired level of family involvement in driving retirement process (part of the driving questionnaire). For longitudinal data, we will examine changes across time points (follow-up at 6, 12, 18, 24 months) and correlation between older driver and family member report.

**Analysis for Aim 2**: We will first test for interaction between DDA effect and each subgroup stratifying factor. We will then use separate stratified subgroup analyses to examine the effects of potential influential cognitive or affective factors on the effect of the DDA (using DCS score, the primary outcome from Aim 1a). As in Aim 1, we will first evaluate demographic characteristics and site effects; all comparisons within subgroups will be between DDA and control groups, using intention-to-treat analysis. The main analysis for each subgroup variable will be an unadjusted test of the intervention by subgroup variable interaction in a statistical model appropriate for the particular outcome (DCS score); specifically, separate multiple logistic models will include intervention group, subgroup, and an intervention-by-subgroup interaction as

AUTO Study Protocol: Version Date: 12/22/21 PI: [name], MPH COMIRB No: 19-0059 factors. Potentially confounding variables (e.g., age, gender) will also be examined in separate multivariable logistic models for each sub-aims.

Aim 2a. Compare the effect of the DDA on decision quality in older drivers with versus without cognitive impairment. Hypothesis 2a: The impact of the DDA will be greater among those without cognitive impairment, as they are able to process the DDA's explanation of facts and options to facilitate a decision. We will examine interaction between cognitive function and the DDA's immediate effect on decision quality (DCS score) by dichotomizing cognitive function into impaired (comprising MCI and dementia) non-impaired. For our initial analyses, we will compare impaired versus non-impaired and run separate simple logistic regression models for each group to determine how cognitive function impacts the relationship between treatment group (DDA or control) and decision quality, as measured by DCS scores. For each cognitive function subgroup, the outcome variable of interest will be the dichotomized decision quality measure (DCS <25 versus DCS  $\geq$ 25), and the intervention group status will be the independent variable. Should we have adequate sample size, we may examine the MCI and dementia subgroups independently.

Aim 2b. Compare the effect of the DDA on decision quality in older drivers with maintained versus impaired decisional capacity. Hypothesis 2b: The impact of the DDA will be greater among those with retained decisional capacity. Decisional capacity scores (range: 0-8) will be examined as a linear variable with controlling for confounding by cognitive function. We will examine the distribution of decisional capacity among the study's 300 participants to define subgroups; participants will be divided into 2-3 subgroups based on decisional capacity scores. As with cognitive impairment above, a simple logistic regression model will be run for each decisional capacity subgroup with dichotomized decision quality measure as the outcome of interest and intervention group status as the independent variable. Additionally, a non-stratified analysis can be conducted in which decisional capacity score is included as an additional independent variable model.

Aim 2c. Compare the effect of the DDA on decision quality in older drivers who are more versus less attitudinally ready for transitions. Hypothesis 2c: The impact of the DDA will be greater in those readier for mobility changes, as defined by lower ARMT scores, as they are "primed" for decision-making (Figures 3.1 and 3.2). We will follow methods similar to Aim 2a, using logistic regression to examine interaction between ARMT score and the DDA's effect on DCS scores by dichotomizing ARMT into high (mean>3.57) versus low/medium (mean 1-3.56). Depending on the distribution of ARMT scores in our sample, we may examine those with low ARMT scores (mean<2.3), as this group may be more open to mobility changes.

Secondary analyses: Additional analyses will include dichotomizing groups based on insight into cognitive function, using the Beck Cognitive Insight Score and following procedures outlined in Aim 2a. We will also examine trajectories of attitudinal readiness to stop driving over time; this will be the first longitudinal study of ARMT scores, and we suspect scores will ultimately decrease (indicating greater readiness for driving retirement) but may first increase (as drivers cope with feeling threatened or worried about the transition). Employing an exploratory trajectory analysis to the data (rather than a recurrent cross-sectional approach) allows us to focus on changes over time for each individual. By following individual trajectories, we are likely to observe factors influencing individuals' decisions rather than have these factors obscured by focusing on recurrent cross-sections of the data. Data will be organized as time-ordered,

AUTO Study Protocol: Version Date: 12/22/21 PI: [name], MPH COMIRB No: 19-0059 sequential matrices (one matrix per unit of analysis). Descriptive statistics for the ARMT scores will be summarized at each time point. In addition, study participants will be grouped into subcategories based on the type of trajectory (both shape and scale) being observed. Intervention group status and its effect on trajectory will be formally explored. Other variables of interest will be assessed in an exploratory manner. Additional secondary analyses will examine interactions between personality factors, ARMT, and the DDA. We will also explore the effect of gender, recognizing that women are more likely than men to self-regulate driving and to stop driving sooner.

**Analysis for Aim 3**: In a mixed-method study with key stakeholders (drivers, family members, healthcare providers, and experts in the field), we will inform future DDA testing and eventual implementation.

Aim 3a. Explore acceptability of the DDA, including recommended modifications.

Aim 3b. Explore views on the ideal settings for DDA use (e.g., clinical setting versus community program). For these qualitative data, we will use a team-based, mixed inductive-deductive approach to review and code transcripts, identify dominant themes, compare themes across content areas, and then group these themes or create sub-themes. We will use "member-checking" to discuss final themes and theme organization with key informants.

Figure 3.

Sample Size: Our target sample size for Aim 1 (n=300 older drivers; 150 DDA and 150 control) was chosen to allow detection of a 20-40% difference between the DDA and control arms (depending on underlying proportions for each of the treatment arms) for the primary Aim 1a measure (DCS score <25; Figure 3.5) at a power of 90% and a 0.05 significance level, while allowing for 10% loss to follow-up. Our overall sample size also allows for stratified

analyses (Aim 2). Estimates for the effect of the driving DDA on behavior among older drivers do not exist, so our assumption of a 20-40% difference is conservative (prior work with other DAs has found an effect size of 40-80% on DCS between groups). For **Aim 2**, pilot work suggests estimates ~30% of participants will have cognitive impairment and 30% will have high ARMT scores (as described above). A stratified sample size of 90 should allow us to detect a 30% difference between the DDA and control groups, at 80% power (see Figure 3). For **Aim 3**, we estimate needing 15-20 interviews per stakeholder group (n=20 older drivers and family members/study partners; n=20 healthcare providers; n=20 experts in the field of older adult driving safety) to reach the "saturation point" (where additional interviews are unlikely to reveal

AUTO Study Protocol: Version Date: 12/22/21 PI: [name], MPH COMIRB No: 19-0059 new themes) while allowing for adequate group diversity. Please note the older drivers and

